1 Diabetic Neuropathy: Function-Structure of Corneal Nerves to Assess Injury - Repair

2

3 Running title: corneal sensitivity and diabetic neuropathy

4

5

6

7 The study is catalogued NCT04222660.

8

9

10 Study Protocol

11 The purpose of this study is to test a new approach for the early detection of DPN.
12 Diabetes patients meeting the criteria were recruited from the Diabetes Clinics and non-diabetic
13 subjects from the general veteran population. A written and informed consent was obtained
14 from all participants. The study adhered to the Declaration of Helsinki and was approved by the
15 Institutional Review Board (#201610799). Participants were divided into two groups: diabetic
16 with peripheral neuropathy and non-diabetic with no history of peripheral neuropathy.

17 Inclusion Criteria: 1) Type 2 diabetes diagnosed based on the opinion of an Endocrinologist,
18 the absence of a history of ketoacidosis, and a C-peptide > 0.8 ng/ml. 2) At least 10 year known
19 duration of diabetes. 3) Age ≥ 50 yr. 4) HbA1c $< 9.0\%$. 5) Mild to moderate PN based on
20 response to Michigan Neuropathy Screening Instrument (MNSI),¹⁸ nerve conduction and
21 amplitude determined using DPNCheck, medical record, presence or absence of ankle reflex,
22 vibration threshold and 10g monofilament sensation. Exclusion Criteria: 1) History of neurologic,
23 muscular, genetic, or other condition known to affect muscle function or exercise tolerance. 2)
24 Electrolyte abnormalities, untreated hypothyroidism, abnormalities in calcium, phosphate, or
25 magnesium concentrations, or any other metabolic disturbance affecting neural function. 3)
26 Cigarette smoking in the past year. 4) Peripheral vascular, cardiac, pulmonary, or any other
27 disorder affecting blood or tissue oxygenation. 5) Use of any medication known to alter
28 peripheral nerve function. 6) History of diabetic foot ulcer. 7) History of corneal disease including
29 dry eye. 8) History of wearing contacts. 9) Any other medical or psychological condition judged
30 to limit compliance with the protocol or interpretation of results.

31 The study included 28 patients with type 2 diabetes and peripheral neuropathy (24 male
32 and 4 female). The average age of the diabetes patients was 66.8 ± 1.9 , with duration of
33 diabetes 20.0 ± 2.6 and hemoglobin A_{1C} 8.2 ± 0.3 . The non-diabetic subjects (11 male and 5
34 female) were younger 49.8 ± 5.0 .

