35 **Clinical neuropathy assessment:** The MNSI questionnaire was self-administered.
36 Each applicant was encouraged to answer yes or no to each of the 15 questions. A score of ≥ 4
37 was considered abnormal. During the MNSI examination a health professional examined the
38 feet, for deformities, dry skin, calluses, infections, and ulcers. Quantitative sensory testing
39 included the presence or absence of ankle reflexes and vibration and monofilament sensation at
40 the dorsum of the great toe.¹⁹ Nerve conduction values were determined using a point of care
41 device *DPNCheck* (*DPNCheck*, NeuroMetrix, Inc., Waltham, MA). Manufacture instructions
42 were followed, briefly after skin preparation, the probes were coated with the conductive gel and
43 applied directly to the skin, posterior to the lateral malleolus.²⁰ Up to four recordings were made
44 as individual tolerance allowed. The recordings were averaged.

45 **Ophthalmic assessment:** All patients underwent a visual acuity assessment. Provided
46 answers to two questionnaires the Ocular Surface Disease Index (OSDI) and Dry Eye
47 Questionnaire (DEQ-5). To evaluate cornea sensitivity each patient underwent a Cochet-
48 Bonnet aesthesiometer examination and blinking response determination following application
49 of a drop of isotonic saline (308 mosmol/liter) or Muro-128 solution 5% sodium chloride (1710
50 mosmol/liter) (Rugby Laboratories, Livonia, MI). This study was performed by having the
51 subject rest their chin comfortably on a support. Three CMOS cameras (Imaging Development
52 Systems GmbH, Obersulm, Germany), one positioned in front of the subject and two positioned
53 laterally, were used to observe both eyes simultaneously. Custom software was used to
54 synchronize video streams and obtain images (MATLAB R2012a, The MathWorks Inc., Natick,
55 MA). Video was taken continuously at 30fps of each subject as an isotonic solution was
56 delivered to the left eye. The response was video recorded for 60 sec after a 10 sec delay.
57 After a 15 min wash and rest period the procedure was repeated using a drop of Muro-128
58 solution 5% sodium chloride. An image collector was used offline to retrieve video frames every
59 10 seconds from each eye drop concentration epoch; therefore 15 images were analyzed
60 subject per solution. Fiji image analysis software was used by a masked technician to measure

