61 the visible surface area of both eyes between the upper and lower eyelids. In each recording
62 epoch, the ratio of time the eyelids were closed are presented as a percentage of the subjects'
63 maximum visible eye surface area between the eyelids during that epoch.

64 **Data Analysis**

65 Results are presented as mean \pm S.E.M. Comparisons between the control and diabetic
66 subjects were conducted using Student t-test (Prism software; GraphPad, San Diego, CA). A p
67 value of less than 0.05 was considered significant.

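### Cheap improvement: use Welch's t-test instead of Student's for groups of 28 and 16, and report each group's SD and n

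*Combined protocol and SAP*

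**What the plan says.** The Data Analysis section has three elements. Results are given as mean and S.E.M. Comparisons of control and diabetic "subjects were conducted using Student t-test (Prism software; GraphPad, San Diego, CA"). A p "value of less than 0.05 was considered significant". The section does not say whether the t-test is the pooled or the unequal-variance form, or whether it is one- or two-sided. It plans no check of spread or shape.

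The participant description under Study Protocol gives the group sizes: "The study included 28 patients with type 2 diabetes and peripheral neuropathy (24 male" and 4 female), and "The non-diabetic subjects (11 male and 5" female), so 28 and 11 + 5 = 16.

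Under Ophthalmic assessment, the blink outcome is a percentage: "the ratio of time the eyelids were closed are presented as a percentage of the" largest visible eye area in that recording. No SD or S.E.M. is given for this or any other eye outcome.

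**The concern.** Student's pooled test combines the two sample variances with weights that follow the group sizes. With equal sizes, the pooled standard error equals the unpooled one whatever the SDs, and the error rate stays close to nominal. With 28 and 16, the larger group dominates the pooled variance.

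If the controls (the smaller group) vary more, the standard error is too small and the test declares differences too often. If the patients vary more, the standard error is too large and real differences are missed. The groups were recruited from different sources, and only the patients faced the diabetes entry criteria (disease duration, HbA1c, neuropathy). Equal outcome spread is therefore an assumption, not something the design secures. A reader cannot tell which case applies, and this test carries the whole inference.

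**Working it through.** **Inputs.** From the documents: n = 28 (diabetic), n = 16 (non-diabetic), threshold 0.05. Assumed: pooled form, two-sided test, one value per subject in each comparison, and the SD ratios and distributions below. The documents contain no power figure or outcome SD, so there is no stated result to reproduce first.

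**Why the sizes matter.** Student's squared standard error is about [(27·s₁² + 15·s₂²)/42]·(1/28 + 1/16). The true value is s₁²/28 + s₂²/16, where s₁ is the diabetic SD and s₂ the control SD.

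- Controls twice as variable (s₁ = 1, s₂ = 2): Student (27 + 60)/42 × 0.0982 = 0.203; true 0.0357 + 0.25 = 0.286. The standard error ratio is √(0.203/0.286) = 0.84, about 16% too small.
- Patients twice as variable (s₁ = 2, s₂ = 1): Student (108 + 15)/42 × 0.0982 = 0.288; true 0.1429 + 0.0625 = 0.205. The ratio is √(0.288/0.205) = 1.18, about 18% too large.

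**Type I error, normal data** (2,000,000 simulated data sets per row, both tests on the same data):

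| Control/diabetic SD ratio | Student | Welch |
|---|---|---|
| 0.5 | 2.2% | 4.9% |
| 0.67 | 3.0% | 5.0% |
| 0.8 | 3.8% | 5.0% |
| 1 | 5.0% | 5.0% |
| 1.25 | 6.5% | 5.0% |
| 1.5 | 7.8% | 5.0% |
| 2 | 9.9% | 5.0% |

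**Power at equal SDs.** For a 0.90 SD difference the noncentrality is 0.90/√(1/28 + 1/16) = 0.90/0.313 = 2.87. The noncentral t on 42 df gives Student 80.1%. Simulation gives Welch 79.3% to 79.4%, depending on the run. Over differences of 0.2 to 1.2 SD the largest loss is 0.80 points.

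**Power at unequal SDs.** Differences are in units of the smaller SD.

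- Patients twice as variable, difference 2.9 × √(4/28 + 1/16) = 1.31: Student 69.4%, Welch 80.7%.
- Controls twice as variable, difference 2.9 × √(1/28 + 4/16) = 1.55: Student 88.2%, Welch 78.6%. Student's apparent lead comes with a 9.9% type I error.

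**Skewed data, equal means.** Assumed SDs are 10 points in patients and 20 in controls, with beta-distributed percentages:

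| Mean | Student | Welch |
|---|---|---|
| 30% | 10.3% | 5.6% |
| 20% | 10.7% | 6.5% |
| 10% | 13.1% | 11.5% |

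Repeat runs put the last Welch figure at 11.5% to 11.8%. Exponential-shaped data with a control/diabetic SD ratio of 2 give 10.8% v 7.3%. With the SDs reversed at mean 10%, Welch is slightly the worse of the two: 5.1% v 5.9%.

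**The case against.** The strongest reply is that no defect has been demonstrated. Every inflated figure above comes from an assumed SD ratio. That stands, and it limits the point to an improvement in method.

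A reader might go further and infer from the ages that the controls do vary more, so that the study's test is too liberal. If the ± values are S.E.M., the age SDs are 1.9 × √28 = 10.1 and 5.0 × √16 = 20.0, a ratio near 2 with the larger spread in the smaller group. But age is not an outcome, and its spread says nothing definite about blink closure or corneal sensitivity. The documents do not support that inference.

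Second, inflation needs equal means with unequal spreads. If the two groups have the same distribution, Student is not inflated even with skew. In four such skewed cases at 28 v 16, Student gave 4.4% to 4.9% and Welch 5.0% to 5.4%. This stands: skew with unequal sizes is not by itself a fault of Student's test, and Welch is then slightly the more liberal.

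Third, the mean 10% beta case is extreme, with about 57% of controls below 1% closure. That is fair. It marks where Welch stops helping and is not a prediction for this study.

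Fourth, the pooled, two-sided form is a reading of the text. The software run may have used the unequal-variance option. If so, stating it settles the choice of test.

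Finally, other problems may matter more. Welch does nothing about the difference in mean age (66.8 v 49.8). The check also assumes one value per subject, while the plan measures "the visible surface area of both eyes between the upper and lower eyelids" and does not say how these are reduced. If both eyes entered as separate observations, neither test would hold its level. Those are limits on what this change achieves, not reasons to keep the pooled test.

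**Conclusion.** The point holds as a low-cost improvement. With 28 and 16 subjects, the only stated test has an error rate that depends on an equality of spread which the documents neither report nor check. For normal data, two-sided testing and assumed SD ratios of 0.5 to 2, the dependence is worth about 2.2% to 9.9% against a nominal 5%, and Welch's test removes it.

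Three stronger statements are not supported. The documents do not show that the study's type I error is inflated, or in which direction it departs from 5%. The cost of under 1 point applies at equal SDs only. And Welch is not a general safeguard: it reaches about 12% in the assumed beta case with mean 10% and SDs of 10 and 20 points. Confidence is medium, because the pooled form is inferred and all SD ratios are assumptions.

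**What to change.** - Use Welch's t-test for the continuous comparisons of control and diabetic subjects, and name the form and sidedness of the test. If Welch was already used, say so.
- Report each group's SD and n for each outcome beside the mean and S.E.M., so that a reader can judge the spread ratio directly.
- For blink closure, show the individual values. If they cluster near 0%, do not rest a conclusion on a p-value close to 0.05.
- The text is in the past tense and recruitment is complete. Describe the change as retrospective unless it was fixed before the data were analysed.
- State that this changes the error rate only and leaves the age difference between the groups untouched.

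The cost is a re-run on existing data with a standard test option, and no new data. In power the cost is under 1 point if the SDs are equal. If they are not, Welch may gain or lose more than that against Student, and where it appears to lose, Student's type I error is above 5%.

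### The stated aim is early detection of neuropathy, but the analysis includes no measure of how well any corneal outcome separates individuals, and significance at 0.05 alone does not show useful detection

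*Combined protocol and SAP*

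**What the plan says.** The Study Protocol section opens with the aim: "The purpose of this study is to test a new approach for the early detection of DPN". It describes two groups, diabetic "with peripheral neuropathy and non-diabetic with no history of peripheral neuropathy", and gives their sizes as 28 and 16.

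The Data Analysis section is three lines long. It says "Results are presented as mean" ± S.E.M., that comparisons between control and diabetic "subjects were conducted using Student t-test (Prism software; GraphPad, San Diego, CA"), and that a p "value of less than 0.05 was considered significant".

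No AUC, sensitivity, specificity, cut-off, SD or confidence interval is specified for the Cochet-Bonnet or lid-closure outcomes. The only score cut-off in the document, 4 or more on the MNSI questionnaire, belongs to the clinical neuropathy assessment and not to the new approach.

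**The concern.** Detection is a statement about individuals: given one person's corneal reading, how reliably can that person be placed in the right group? A t-test asks whether two group means differ. At a given sample size, a significant result is compatible with anything from weak to excellent separation, and the significance label does not say which.

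Presenting the data as mean ± S.E.M. does not help. The S.E.M. describes the precision of the mean and is smaller than the SD by a factor of √28 = 5.3 in one group and √16 = 4.0 in the other. The spread between people, on which detection depends, is not shown.

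At stake is the interpretation of the main result. A measure could reach p < 0.05 and be read as support for a detection method although it separates people poorly. A measure that separates them well could be reported without the figure that shows it.

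**Working it through.** The document states no accuracy, power or sample-size figure, so there is none to reproduce. The check asks what level of separation the significance rule demands.

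**Inputs from the document**
- Diabetic group: 24 male + 4 female = 28 (Study Protocol).
- Non-diabetic group: 11 male + 5 female = 16 (Study Protocol).
- Student t-test, alpha 0.05 (Data Analysis).

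**Assumptions.** Two-sided test (the document does not say), normal data, equal SDs, all 44 analysed, and the observed difference taken as the true one.

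**Smallest significant difference**
- df = 28 + 16 − 2 = 42; t(0.975, 42) = 2.018.
- d = 2.018 × √(1/28 + 1/16) = 2.018 × 0.313 = 0.632 SD.

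**What that means for individuals**
- AUC = Φ(d/√2) = Φ(0.447) = 0.673.
- Correct classification at the midpoint cut-off = Φ(d/2) = Φ(0.316) = 62.4%, the same for sensitivity and specificity.
- Overlap of the two distributions = 2Φ(−d/2) = 75%.
- Hanley-McNeil standard error of the AUC = 0.082, so the approximate 95% CI is 0.673 ± 1.96 × 0.082 = 0.51 to 0.83.

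**How far the 62% moves with the assumptions**

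| Variant, result exactly at the threshold | Correct |
|---|---|
| Two-sided t, equal SDs, midpoint cut-off | 62.4% |
| Normal approximation in place of t | 62.1% |
| One-sided test | 60.4% |
| Cut-off tuned to the 28:16 mix | 66.7% |
| SD ratio (diabetic to control) 0.5, best balanced accuracy | 66.4% |
| SD ratio 2, best balanced accuracy | 68.1% |

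For the tuned cut-off, the benchmark is 28/44 = 63.6%, which is what calling everyone diabetic achieves.

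**For contrast.** To classify 80% correctly at the midpoint, d must be 2 × 0.842 = 1.68. With these groups that gives t = 1.68/0.313 = 5.37 and p of about 3 × 10⁻⁶. Such a result and one at p = 0.049 would both simply be significant under the plan.

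**Age, which bears on the remedy.** Mean ages are 66.8 ± 1.9 and 49.8 ± 5.0. The ± is not labelled there. If it follows the stated S.E.M. convention, the SDs are 1.9 × 5.29 = 10.1 and 5.0 × 4 = 20, and the pooled SD is √[(27 × 10.05² + 15 × 20²)/42] = 14.4. Then d = 17.0/14.4 = 1.18, and age alone would classify Φ(0.59) = 72% correctly.

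**The case against.** The strongest reply is that the information is not lost. With n fixed, t converts directly to d, and the SD is the S.E.M. times 5.3 or 4.0. A reader with mean, S.E.M. and n can therefore approximate d and the AUC, and can rank the measures. This stands. A reader might infer that the planned output makes measures impossible to compare; the document does not support that, because it promises means and S.E.M. as well as a p-value. But the conversion depends on normality, which is not assured for a bounded percentage such as lid closure, and the plan does not commit to making it.

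A reader might also infer that separated S.E.M. bars hide almost complete overlap between people. That goes too far. The bars just touch at d = 1/5.29 + 1/4 = 0.44, where overlap is 2Φ(−0.22) = 83%, and overlap falls as they separate. It is still large at the significance threshold (75%).

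Nor does any section say that p < 0.05 will be taken as proof of detection ability. The text is compatible with a first group comparison, although it does not describe itself as one. That makes the harm a risk of interpretation, not a stated intention.

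Finally, an AUC from these groups has its own weakness. It contrasts older patients with established neuropathy against younger non-diabetic people, so part of it may reflect age. This stands, and the remedy has to allow for it.

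**Conclusion.** The point holds as a gap between aim and analysis: a detection aim with no planned measure of discrimination. The t-test is not invalid for comparing means, but it does not by itself answer the stated question.

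The 62% figure (AUC 0.67) describes a result exactly at p = 0.05 under the listed assumptions; the range is about 60% to 68% when they are varied. It would be wrong to infer that the corneal measures misclassify more than a third of people. The document contains no corneal results, and actual accuracy may be higher. It would also be wrong to treat an AUC from this sample as an upper bound on performance in practice. With 44 people its interval is wide, so likely optimistic is as much as can be said.

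**What to change.** For Cochet-Bonnet and each lid-closure measure:

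- Plot individual values and give the SD by group.
- Give the mean difference with its 95% CI.
- Give the ROC AUC with its 95% CI (DeLong or bootstrap).
- Add an age-adjusted AUC or an age-adjusted group comparison as a sensitivity analysis.
- If sensitivity is reported, give it at a specificity that 16 controls can attain: 14/16 = 87.5% (exact 95% CI about 62% to 98%) or 15/16 = 93.75% (about 70% to 99.8%). Exactly 90% is not attainable. Give exact intervals and call the result descriptive, since the cut-off rests on one or two people.

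Base any statement about detection on the AUC interval rather than on p < 0.05. Describe the AUC as likely optimistic, because cases have established neuropathy and controls are younger and non-diabetic. The document is written in the past tense, so label the AUC post hoc if it is added after the data were seen.

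The cost is a few lines of plan text, a short extra analysis of existing data, and a wide interval to report. No new participants or procedures are needed.
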